3.3 Randomization

After informed consent was obtained, qualifying infants were randomized by 6 hours of age to either hypothermia or the non-cooled control group. Randomization occurred 24 hours a day, 7 days a week through the Data Coordinating Center at RTI International, Research Triangle Park, NC. Infants were stratified by center and degree of NE (moderate versus severe). In the unlikely event of a multiple gestation qualifying for inclusion, all who qualified were randomized independently.

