4.1 Modeling Processes, Prior Specification, and Reporting Procedures

- For binary outcomes, the protocol specified that a Bayesian log-binomial regression model with random center effect would be fit to estimate the relative risk of hypothermia relative to normothermia. However, since the protocol was written, an increasing emphasis has been placed on including inference on risk differences in clinical trial reports, so a logistic regression model with random center effect will be fit followed by post-processing of individual predicted probabilities of outcome to estimate posteriors of relative risk and risk differences.¹
 - Weakly informative priors will be used during analyses to better understand the effect of hypothermia on outcomes considered in this trial:
 - On the relative risk and risk difference scales of primary outcome and components, the priors for the treatment effect will include a skeptical prior, a neutral prior, and an enthusiastic prior. For all other outcomes, only the neutral prior will be used.
 - For the intercept and the encephalopathy terms, broad neutral priors will be used.
 - For the random center effect, a Normal prior centered at 0 will be used where the standard deviation parameter of this prior will have a half-normal hyperprior with mean equal to 0 and standard deviation equal to 1.
 - Further details about these priors are given in section 6.4.2 and 6.4.3
 - Posterior distributions, posterior means, posterior probabilities of benefit, and 95% credible intervals will be reported for the effect of hypothermia on the outcomes considered.
- For count outcomes such as days or durations, a negative binomial model with random center effect will be fit to estimate relative risk.
 - Weakly informative priors will be used during analyses to better understand the effect of hypothermia on outcomes considered in this trial:
 - On the relative risk scale, the priors for the treatment effect will include a neutral prior.
 - For the intercept and the encephalopathy terms, broad neutral priors will be used.
 - For the random center effect, a Normal prior centered at 0 will be used where the standard deviation parameter of this prior will have a half-normal hyperprior with mean equal to 0 and standard deviation equal to 1.
 - Further details about these priors are given in section 6.4.2 and 6.4.3

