Model parameter estimates will be generated by fitting three MCMC chains. Each chain will involve at least 10,000 burn-in samples and at least 200,000 additional samples, which will be thinned by at least 5. More samples and more thinning will be done if necessary, to produce good sampling of the posterior. The final MCMC chains will have at least 120,000 useable samples to estimate the posterior distributions necessary for making inference about the treatment effects, (relative risk or outcome difference).

For binary outcomes, the outcome for the j^{th} infant from the i^{th} center will have the following form:

$$y_{ij} = \begin{cases} 0 & \text{survival without moderate / severe disability at 18-22 months corrected age} \\ 1 & \text{death or moderate / severe disability at 18-22 months corrected age} \end{cases}$$

The main covariates will have the form:

$$trt_{ij} = \begin{cases} 0 & \text{normothermia} \\ 1 & \text{whole body hypothermia} \end{cases}$$

$$enceph_{ij} = \begin{cases} 0 & \text{mild encephalopathy} \\ 1 & \text{moderate or severe encephalopathy} \end{cases}$$

The logistic model used for analysis of binary outcomes on the relative risk and risk difference scale will have the following form:

$$y_{ij} \sim \text{Bernoulli}[\pi_{ij}], \text{ where}$$

$$\text{logit}[\pi_{ij}] = \alpha_i + \theta_1 \cdot \text{enceph}_{ij} + \theta_2 \cdot \text{trt}_{ij}$$

β_1, β_2 will have priors as specified in Section 6.5.3

α_i will be the random intercepts due to center. Prior specified in Section 6.5.3.

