The prior for the random center effects will be Normal centered at 0, and the hyperprior for the standard deviation of the random center effect will be specified in Section 6.5.3. Any baseline covariates that are added to the model (in sensitivity analyses to adjust for important unbalanced baseline covariates) will either be coded using 0/1 indicator variables, sets of indicator variables, or as centered continuous covariates. Priors for these other to-be-determined covariates are specified in Section 6.5.3. Post processing will be used to get posterior approximations of relative risk and risk differences due to treatment. The logistic model will be fit to the data, then for each infant, the model parameter chains will be used to estimate the within subject posterior relative risk and risk difference which will equal hypothermia divided by normothermia and hypothermia minus normothermia respectively. A within subject estimate of relative risk will be calculated by setting

the treatment variable value to hypothermia, estimating the probability of outcome for all infants, repeating the same process after setting the treatment variable to normothermia then dividing the two probabilities of outcome for all infants, hypothermia over normothermia. A within subject estimate of risk difference will be calculated by setting the treatment variable value to hypothermia, estimating the probability of outcome for all infants, repeating the same process after setting the treatment variable to normothermia then subtracting the two probabilities of outcome for all infants, hypothermia minus normothermia. Since the parameter chains will contain at least 120,000 samples, each infant will contribute at least 120,000 samples for the approximation of the within subject relative risk posterior and the within subject risk difference posterior. Using all samples of relative risk and risk differences from all infants to approximate the posteriors, the mean estimate of relative risk and risk difference will be calculated as well as, 95% credible intervals of mean relative risk and risk difference. Finally, posterior probabilities of benefit due to hypothermia from both relative risk and risk differences will be used as summary statistics. Differences in the relative risk and risk difference posteriors will be reflected upon to better understand the estimated treatment effect.

For count outcomes like days or duration, y_{ij} , the main covariates will have the form:

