6.5.5 Final Analysis

The final analysis will occur after 168 infants have completed the trial, as specified earlier. The final analysis will not occur until all enrolled infants have a primary outcome determination, i.e. have the primary endpoint value assigned, classified as withdrawn without primary outcome assigned, or deemed lost to follow-up. Part of determining primary outcome of enrolled infants will involve masked adjudication of outcomes for infants who have an indeterminable outcome based on partially collected follow-up information. Once all enrolled infants have reached final status and primary endpoints determined, the clinical database will be exported, and study analysis datasets created. At that point, the analysis datasets will be considered “locked” and any further adjustments to the clinical datasets will not be included in the analysis datasets.

The final analysis will involve posterior distribution estimation for the effect of hypothermia relative to normal cooling. For binary outcomes, the effect will be the adjusted relative risk and adjusted risk differences calculated from a binomial regression model with logit link and post processing of

predicted outcome probabilities. For count outcomes, the effect will be the adjusted relative risk from the two groups obtained using negative binomial regression. For ordinal outcomes, the effect will be the adjusted odds ratio calculated from the cumulative logits.

For treatment relative risk estimation, posterior probabilities of >0%, >5%, >10% and >20% decrease in binary outcomes will be calculated. If θ is the relative risk defined as risk in cooling group over risk in control group, then the above specified posterior probabilities are, $\Pr(\theta < 1 | X)$, $\Pr(\theta < 0.95 | X)$, $\Pr(\theta < 0.9 | X)$, $\Pr(\theta < 0.8 | X)$. In addition to posterior probability calculations, graphical displays of the posterior distribution and appropriate 95% credible intervals for the over-all relative risk will be created. Finally, forest plots of the center level relative risks and 95% credible intervals will be created.

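### SAP 6.5.1 pools every infant's posterior draws, so the intervals, SDs and graded benefit probabilities do not describe the over-all relative risk and risk difference

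*SAP*

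**What the plan says.** SAP 4.1 replaces the protocol's log-binomial model with a logistic model whose predicted probabilities are post-processed into RR and RD. It promises: "Posterior distributions, posterior means, posterior probabilities of benefit, and 95% credible intervals will be reported".

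SAP 6.5.1 gives the steps. Each infant's outcome probability is predicted under hypothermia and under normothermia, and the two are divided and subtracted. Then "each infant will contribute at least 120,000 samples for the approximation of the within subject relative risk posterior", and likewise for RD. The next step is "Using all samples of relative risk and risk differences from all infants to approximate the posteriors". From that collection come the mean estimates and the "95% credible intervals of mean relative risk and risk difference".

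SAP 6.5.5 names the target again: "graphical displays of the posterior distribution and appropriate 95% credible intervals for the over-all relative risk will be created", with a parallel sentence for RD. It describes the RR as "relative risk defined as risk in cooling group over risk in control group". For each of the six primary-outcome analyses it lists a posterior plot, median, SD, 95% credible interval and graded threshold probabilities. SAP 6.5.8 adds contrasts of treatment effects between subgroup levels.

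No section says that the infant-level effects are averaged within a draw before these summaries are taken.

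**The concern.** The target is one over-all effect, and its posterior has one value per draw. The written steps give one value per infant per draw and treat the whole collection as the posterior. Infants differ in baseline risk by centre, and by encephalopathy level if that varies, so under a logistic model they differ in RR and RD even though the odds ratio is common. That spread is real, but it is not uncertainty about the over-all effect.

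At stake are the credible intervals, SDs, plots, medians (to a lesser degree) and every threshold probability other than the one at the null. SAP 3.4 justifies a trial without conventional power by the precision of its effect estimate, so misreporting that precision matters here.

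**Working it through.** **Plan's own figure.** Three chains × 200,000 samples ÷ thinning of 5 = 120,000 retained draws, as 6.5.1 states. Each infant's contribution is therefore the whole retained chain. With 168 infants the literal pool holds 168 × 120,000 = 20,160,000 values.

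**Algebra.** Let θ(i,s) be the RR or RD for infant i at draw s.

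- Target: θ̄(s) = mean over i of θ(i,s), then summarise across s.
- Literal text: summarise all θ(i,s) together.
- Var(pool) = Var over s of θ̄(s) + mean over s of the between-infant variance of θ(i,s).

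The second term is the surplus. The two means are equal. Within a draw the treatment coefficient has one sign, so all infants have RR<1 or none do. Pr(RR<1), Pr(RD<0, hypothermia minus normothermia) and exclusion of the null by the 95% interval are therefore the same either way.

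**Worked example.** One simulated trial, illustrative only.

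- From the SAP: 168 infants, 18 centres, the 6.5.3 priors with the neutral treatment prior, and risks of about 70% against 50%.
- Assumed: centre SD 0.5 on the logit scale, 30% severe, log odds ratio 1.5 for severe against moderate.
- The model was fitted by Hamiltonian Monte Carlo, and both summaries use the same draws.

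| | Pooled | Averaged within draw |
|---|---|---|
| RR mean / median | 0.809 / 0.827 | 0.809 / 0.803 |
| RR SD | 0.134 | 0.096 |
| RR 95% interval | 0.524 to 1.011 | 0.638 to 1.017 |
| RD SD | 0.073 | 0.063 |
| RD 95% interval | −0.269 to 0.007 | −0.237 to 0.009 |
| Pr(RR<1) | 0.968 | 0.968 |
| Pr(RR<0.9) | 0.700 | 0.830 |
| Pr(RD<−0.05) | 0.805 | 0.854 |

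The surplus RR variance is 0.134² − 0.096² = 0.0087, almost as large as the posterior variance of the mean effect (0.096² = 0.0092). The RR interval is 0.487/0.379 = 1.28 times as wide and the RD interval 0.277/0.246 = 1.13 times. All the extra RR width lies on the side away from 1.

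Across six such scenarios the RR interval was 7–28% wider and the RD interval 1–13% wider. With a constant encephalopathy term and centre SD 0.3 the gap was small: RR width 0.427 against 0.398, RD 0.272 against 0.268. In a 70%-to-60% scenario Pr(RR<0.8) moved the other way, 0.145 pooled against 0.122 averaged.

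**Range over assumptions.** The SAP does not give the following, so they are assumed:

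- severe fraction 20, 25 or 30%;
- control risks (moderate/severe) 0.6/0.9, 0.65/0.85 or 0.3/0.8;
- odds ratio 0.41, 0.64 or 1.0;
- centre SD 0, 0.3 or 0.6, with unequal centre sizes.

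That gives 81 scenarios × 40 trials × 2 codings = 6,480 fits, by Laplace approximation. Two codings are needed. SAP 6.5.1 gives the value 1 to "moderate or severe encephalopathy" and 0 to mild, so the term is constant in a trial that enrols only moderate and severe cases. Section 3.3, by contrast, says: "Infants were stratified by center and degree of NE (moderate versus severe". Entries below are ranges of scenario averages; RR widths are on the log scale.

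| Pooled against averaged | Coding as printed | Moderate/severe coding |
|---|---|---|
| RR interval wider by | 2–30% (median 8%) | 10–47% (median 21%) |
| RD interval wider by | 0.5–8% (median 2%) | 3–18% (median 8%) |
| Mean absolute shift, Pr(RR<0.9) | at most 0.035 | 0.01–0.09 |
| Mean absolute shift, Pr(RR<0.8) | at most 0.05 | 0.01–0.10 |
| Mean absolute shift, Pr(RD<−0.05) | at most 0.012 | 0.005–0.035 |
| Share of the over-all RR posterior inside the pooled 95% interval | 95.4–97.6% | 96.6–98.6% |

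The largest values come from odds ratio 0.41. Without it the upper ends are RR 17% and RD 5% (as printed), RR 30% and RD 13% (moderate/severe).

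Pr(RR<1) was identical in every fit. Exclusion of 1 differed in 6 of 6,480 fits, all with a limit within 0.001 of 1, which is quantile interpolation. Importance-sampling correction gave slightly more widening than Laplace (for example 16% against 14%), so the table does not overstate the effect. A separate Hamiltonian Monte Carlo check at centre SD 0.3 gave RR widening of 5–14% as printed and 10–21% with moderate/severe coding.

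**Which RR.** The infant-level ratio in 6.5.1 points to the mean of infant RRs. The 6.5.5 definition can be read as the ratio of mean risks. Their posterior means differ by up to 0.01 as printed and 0.045 with moderate/severe coding; in the worked example they are 0.809 and 0.830.

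**The case against.** The sentence goes on to speak of intervals of the mean, and an interval of a mean presupposes one mean per draw. The paper cited in 4.1 is about average predictive comparisons, and 6.5.5 speaks of an over-all effect. On this view the target is fixed and only the mechanics are loosely worded. No decision rule rests on the SD, the interval width or the graded probabilities, the one probability with a stated goal is Pr(RR<1) in 3.4, and under the printed coding the distortion is small.

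Much of this stands. Averaging may well have been intended, and nothing here shows what was run. The null-based results are safe, and the larger figures apply only if the encephalopathy coding is changed. Under the printed coding, without added covariates, all infants in a centre share the same effect in each draw, so the centre forest plots are unaffected. For the 6.5.8 contrasts, draws can still be matched by iteration; the pool alone just does not supply the one effect per draw and subgroup level that they need.

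It does not remove the point. A programmer following the written steps would pool, and the result would carry the label of a different quantity. Nor is pooling simply conservative, because the graded probabilities move both ways.

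**Conclusion.** The point holds. As written, 6.5.1 produces intervals, SDs and graded benefit probabilities that do not describe the mean or over-all RR and RD named as the target. That pooled variance exceeds the target variance whenever infant effects differ follows from algebra; only the size rests on the assumed risks, severity mix and centre variation. With the printed coding the typical effect is modest (median widening 8% for RR, 2% for RD). It is larger if encephalopathy is coded moderate against severe. The harm is confined to reported precision and the graded statements. The unspecified choice of over-all RR is a lesser, separate gap. The text should be corrected, but the direction of the trial's conclusion is not at risk.

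**What to change.** In 6.5.1, state that for each posterior draw RR and RD are averaged over infants, giving one over-all RR and one over-all RD per draw. State also that the mean, median, SD, 95% credible interval, plot and all threshold probabilities are taken across the at least 120,000 draws. Apply the same rule within subgroup level and within centre; the latter matters only if encephalopathy or other covariates vary within a centre. Say whether the over-all RR is the mean of infant RRs or the ratio of mean risks; that choice is the sponsor's.

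The cost is one or two sentences and one averaging line in the post-processing. No model is refitted. The posterior mean RD, the mean of infant RRs and Pr(RR<1) stay as they are.

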1.3 SAP Revision History

Ver.	Justification for change	Date
0.1	Initial Version	2021-05-3
0.2	2 nd draft	2021-10-05
0.3	3 rd draft	2021-12-03
0.4	4 th draft	2022-06-13
0.6	6 th draft	2022-09-13
0.7	7 th draft	2022-10-18
1.0	Approved	2022-11-02
1.1	Per study subcommittee deliberation over email on March 3 rd and 4 th , 2023, changed the model used for analysis of ordinal outcomes from a proportional odds model to a set of logistic regression models with post processing to facilitate calculations of relative risks and/or risk differences. This change made the analysis more consistent with the analysis of previous hypothermia trials.	2023-01-02

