4.3 Analysis Datasets

This analysis will use two analysis populations, a full analysis set (FAS) and per-protocol (PP).² The FAS analysis population will include all randomized infants with ascertained primary outcomes. This FAS analysis population is recognized as being as close as possible to an intent-to-treat population. All analyses based on the FAS will analyze infants as randomized. The PP analysis population will include all infants who received their randomized treatment (72 hours of hypothermia or normothermia) and have a determined primary outcome. All analyses based on the PP will analyze infants as treated.

² ICH E9: <https://www.fda.gov/regulatory-information/search-fda-guidance-documents/e9-statistical-principles-clinical-trials>

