$$trt_{ij} = \begin{cases} 0 & \text{normothermia} \\ 1 & \text{whole body hypothermia} \end{cases}$$

$$enceph_{ij} = \begin{cases} 0 & \text{mild encephalopathy} \\ 1 & \text{moderate or severe encephalopathy} \end{cases}$$

The model used for analysis of day and duration outcomes will have the following form:

$$y_{ij} \sim \text{NegBinomial}[\vartheta_{ij}], \text{ where}$$

$$\ln(\vartheta_{ij}) = \alpha_i + \theta_1 \cdot enceph_{ij} + \theta_2 \cdot trt_{ij}$$

β_1, β_2 will have priors as specified in Section 6.5.4

α_i will be the random intercepts due to center. Prior specified in Section 6.5.4.

The prior for the random center effects will be Gaussian centered at 0, and the hyperprior for the standard deviation of the random center effect will be specified in Section 6.5.4. Any baseline covariates that are added to the model (in sensitivity analyses) will either be coded using 0/1 indicator variables, sets of indicator variables, or as centered continuous covariates. Priors for these other to-be-determined covariates are specified in Section 6.5.4.

The analysis of ordinal outcomes will use sets of logistic regression models as used for binary outcomes. One of the ordinal outcome levels will be designated as the reference level, and then logistic regression models will be fit to subsets of the data where one group of included data will be records that equal to reference level and the other group of included data will be records that equal one of the other outcome levels. For example, if an ordinal outcome has 3 levels, with level 3 designated as the reference level, then two logistic regression models will be fit:

- One model will use data from level 1 and level 3
- The second model will use data from level 2 and level 3

The prior for the random center effects will be Normal centered at 0, and the hyperprior for the standard deviation of the random center effect will be specified in Section 6.5.3. Any baseline covariates that are added to the model (in sensitivity analyses) will either be coded using 0/1 indicator variables, sets of indicator variables, or as centered continuous covariates. Priors for these other to-be-determined covariates are specified in Section 6.5.3.

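### For outcomes analysed as ordinal, relative risks and risk differences formed from the pairwise subset models are conditional on the outcome and are not contrasts of each level's risk

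*SAP*

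**What the plan says.** Section 1.3 records that version 1.1 replaced the proportional odds model with "a set of logistic regression models with post processing to facilitate calculations of relative risks and/or risk differences". Section 6.5.1 carries this out: "The analysis of ordinal outcomes will use sets of logistic regression models as used for binary outcomes". The data rule follows: "logistic regression models will be fit to subsets of the data", one group being the records at the reference level and the other group the records at one other level. In the SAP's three-level example with level 3 as reference, "One model will use data from level 1 and level 3", so infants at level 2 are left out of that model. The text does not say which level of any actual outcome is the reference.

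For binary outcomes, 6.5.1 obtains the RR by predicting each infant's probability under hypothermia, "repeating the same process after setting the treatment variable to normothermia then dividing the two probabilities of outcome for all infants"; the RD is the matching subtraction. No step turns pairwise probabilities back into probabilities over all levels.

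Other text was not updated. Section 6.5.1 also still names proportional odds models for ordinal outcomes, 6.5.3 sets priors for them, and 6.5.5 gives the ordinal effect as a cumulative-logit odds ratio, both in general and for ordinal safety outcomes.

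**The concern.** Which infants enter each model is decided by their outcome, which treatment can change. The share of each arm that is kept can therefore differ between arms, and the denominator is no longer the group that was randomized and assessed. If hypothermia moves infants into or out of the reference level, a different level with the same frequency in both arms will appear to be reduced or increased.

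This matters because RR and RD are the stated reason for the change of method. A reader of the trial report would take an RR for mild disability as a comparison of how often mild disability occurred in the two arms. The pairwise figure does not measure that. Section 4.3 says "All analyses based on the FAS will analyze infants as randomized". The pairwise models keep the randomized labels but compare arms that have been filtered by outcome.

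**Working it through.** There is no SAP figure to reproduce, and the SAP gives no level probabilities by arm. All rates below are assumptions, written normothermia versus hypothermia.

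**What the subset model estimates.** For level k and reference level ref, a logistic model fitted only to infants at k or ref estimates, in each arm,

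q_k = p_k / (p_k + p_ref).

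- RR from the subset = (p_k,hypo / p_k,normo) × (p_k,normo + p_ref,normo) / (p_k,hypo + p_ref,hypo). It equals the true RR only when the included share p_k + p_ref is the same in both arms.
- RD from the subset in general equals the true RD only when p_k + p_ref = 1 in both arms, that is, when nobody is dropped.
- Odds q_k/(1 − q_k) = p_k/p_ref, so the subset odds ratio is exactly the baseline-category odds ratio.

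**Main example.** None 40% vs 55%, mild 20% vs 20%, moderate/severe 40% vs 25%.

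- True RR for mild: 0.20/0.20 = 1.00; true RD 0.
- Subset with none as reference: q = 20/60 = 0.333 vs 20/75 = 0.267. RR = 0.267/0.333 = 0.80; RD = −0.067.
- Subset with moderate/severe as reference: q = 20/60 = 0.333 vs 20/45 = 0.444. RR = 1.33.
- Odds ratio, mild against none: (20/55)/(20/40) = 0.73. This is correct as a baseline-category odds ratio.

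So a level with equal risk in both arms gives 0.80 or 1.33 according to the reference chosen.

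**Smaller shift.** None 40% vs 45%, mild 20% vs 20%: (20/65)/(20/60) = 0.308/0.333 = 0.92.

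**Other assumed rates.**

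- Four levels, severe/moderate/mild/none: 30/15/25/30% vs 30/10/15/45%. Severe, true RR 1.00 and RD 0; subset (30/75)/(30/60) = 0.40/0.50 = 0.80, RD −0.10.
- Reversal of direction, three levels with the third as reference: 40/40/20% vs 44/16/40%. Level 1, true RR 1.10 and RD +0.04; subset (44/84)/(40/60) = 0.524/0.667 = 0.79, RD −0.143.
- Equal included share, four levels: 30/15/25/30% vs 20/15/25/40%. Severe plus none is 60% in both arms. True RR 0.67, subset RR 0.67; but the RD is −0.167 against a true −0.10.

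**Does predicting for all infants repair it?** Section 6.5.1 averages predictions over all infants, so this was checked by simulating 400,000 infants with a binary encephalopathy covariate and equal level 1 risk by arm within each covariate level, without center effects or priors. The subset model was fitted and its predictions averaged over everyone. Simulated level 1 risks were 0.311 vs 0.309 (RR 1.00). The averaged predictions were 0.544 vs 0.414, with RR 0.75 and RD −0.130; 56.5% vs 74.9% of infants had entered the fit. The coefficients come from the selected subset, so averaging over all infants does not restore the risk of the level.

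**The case against.** The strongest reply is about reach. The primary outcome is binary. The only clearly ordinal outcome in the visible text is disability in survivors in 6.4, and the same section lists severe, moderate, mild, no, and moderate-or-severe disability among survivors as separate binary outcomes, and the Bayley bands likewise. Those use the ordinary binary model with all assessed survivors in the denominator, so the true RR of 1.00 for mild in the example would be available there. Bowel perforation and cause of death have several levels but are nominal. All of this stands and limits the point, although two different RRs could then be reported for the same level in the same survivors.

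A second reply is that the ordinal paragraph of 6.5.1 does not itself say that RR and RD will be formed, while 6.5.5 names a cumulative-logit odds ratio. That also stands in part: the RR/RD step is inferred from the stated purpose in 1.3, from the reference to the binary-outcome models, and from 6.5.5, which sends secondary outcomes through the same process as the primary. The inference is fair, but the effect measure is not settled in the text.

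A reader might infer that the pairwise fits are invalid altogether, or that the trial's main result is distorted. The SAP supports neither: the pairwise odds ratio is sound, and the primary analysis does not use these subsets.

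**Conclusion.** The rule is wrong as written for RR and RD, within a narrow scope. If those measures are formed from the pairwise subset models, as section 1.3 intends, they are conditional on ending at level k or the reference level and change with the reference chosen. Under the assumed rates with mild at 20% in both arms and none as reference, the RR for mild is 0.92 with a 5-point shift into the reference level and 0.80 with a 15-point shift, against a true 1.00; reversal of direction is possible. Where the included share is equal between arms the RR is undistorted, but the RD is still off. The size in this trial cannot be known from the SAP.

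The conclusion does not extend to the primary outcome, to the binary disability outcomes, or to the pairwise odds ratio. It should be corrected together with the contradiction over the ordinal model and effect measure.

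**What to change.** Choose one of two routes and state it in 6.5.1:

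- Keep every infant in the analysis set in each model (all assessed survivors for survivor outcomes), with the outcome coded as level k versus all other levels or as cumulative splits, and derive RR and RD with the existing post-processing. For disability in survivors this largely coincides with the binary outcomes already in 6.4, so the text can point to them. Survivor results remain conditional on survival and should be labelled so.
- Or keep the pairwise fits, name the reference level for each outcome, and report only an odds ratio labelled as baseline-category, with no RR or RD from those fits.

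Then align the proportional-odds statement in 6.5.1, the prior text in 6.5.3, and the cumulative-logit and proportional-odds statements in 6.5.5 with the route chosen. The cost is SAP wording and, for the first route, a changed data filter; the logistic models, priors and software stay the same.
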